### **PET Data Acquisition and Analysis**

Subject preparation consists of intravenous (IV) catheterizations for IV administration of the radiotracer and blood sampling. Risks of radial artery cannulation are minimized by having the procedure performed by an experienced health care provider. The health care provider would be either a physician or an advanced practice registered nurse (APRN) with experience in critical care and placement of arterial catheters, as is the practice at Yale-New Haven Hospital. For an APRN to place the arterial line at the Yale PET Center, they must meet the following criteria:

- 1.) Be currently credentialed at Yale-New Haven Hospital or similar institute and
- 2.) Perform 3 arterial line procedures supervised by a currently privileged PET Center physician

The 3 supervised arterial line placements will be documented and signed off by both the APRN and supervising physician. The completed document must be on file at the Yale PET Center prior to an APRN performing any arterial line catherizations independently.

The site will be anesthetized with lidocaine prior to arterial line insertion. The arterial line may remain in place for the whole day of scanning, after which it will be removed by trained nursing staff at the Yale PET Center. PET data are acquired while subjects rest with an HRRT PET scanner (207 slices, resolution better than 3 mm FWHM). A transmission scan will be obtained for each emission scan. Motion correction may be performed dynamically with measurements from the Vicra (NDI Systems, Waterloo, Ontario) used by a dedicated list-mode reconstruction algorithm. Acquisition of list-mode emission data will begin shortly before IV administration of up to 20 mCi of high-specific activity [C]ABP688 or up to 5 mCi of high-specific activity [F]FPEB and will continue for up to 120 minutes post-injection for [C]ABP688 or up to 180 minutes post-injection for [F]FPEB. Dynamic images of radioactivity concentration will be reconstructed with corrections for measured attenuation, normalization, random events, scatter, and deadtime. Subjects will be asked to void after the scan is completed to reduce radiation exposure to the bladder. Venous blood samples to measure plasma blood alcohol concentration (BAL) and peripheral cytokine levels will also be acquired. After the completion of the days final PET scan, the IVs will be removed. Monitoring of vitals will continue for at least 30 minutes before subject returns to the CNRU or HRU.

List mode data will be reconstructed with MOLAR^43, with corrections for attenuation, normalization, and motion to create high resolution images. Early PET image data will be registered to the subjects T1-weighted

MR image. The T1-weighted MR image will be non-linearly registered to MNI space for region of interest (ROI) identification. ROIs will be selected using the Anatomical Automatic Labeling template for SPM8. To minimize possible partial volume effects, only gray-matter voxels will be included in ROI definition based on MRI segmentations performed with the Computational Anatomy Toolbox. Since glutamate release has been observed throughout the brain, ROI analyses will focus on the primary brain regions of frontal, parietal, temporal, and occipital cortices; striatum, amygdala, hippocampus, thalamus, and cerebellum. The primary outcome measure will be [C]ABP688 or [F]FPEB  $V_T$  estimated with the 2-tissue compartment model as previously validated, which yields a test-retest variability of <12%.

#### Laboratory Alcohol Session

Laboratory sessions will occur at the Yale PET Center. Subject body weight will be acquired during intake as part of the medical history and used for alcohol dose calculations. Subjects will be asked not to diet between intake and study days. Alcohol dose will be recalculated if the subject's weight varies by more than 5 pounds for women and 10 pounds for men. Confirmation of alcohol abstinence will be made via self-report and breathalyzer on study day. Subjects will be given a light standardized breakfast on arrival to the laboratory and the morning prior to discharge.

Prior to alcohol administration, subjects will have a standardized light lunch to increase tolerability of the alcohol dose while minimizing the potential for variations in food intake that could affect alcohol metabolism.

Oral alcohol challenge: Alcohol will be administered in the form of 80 proof vodka and a mixer based on the subject's choice of water or a decarbonated noncaffeinated noncaloric soda. The dose will be prepared by the research team and take into account the participant's total body water (based on gender, age, height, and weight), duration of drinking, and ratio of alcohol to mixer, based on Watson et al's update of the Widmark equation. The total volume will be divided into three equal drinks, with each consumed over a 10-minute period to control the rate of consumption. This pacing aims to reduce risk of nausea. After the session subjects may drink water ad lib until scanning. Subjects will be asked to void prior to the second PET scan. Afterwards, subjects will be given dinner based on food preferences. Water, crackers, and other snacks will be available ad lib for the rest of the evening.

I.V. Alcohol Challenge: An antecubital IV line will be placed in one arm, contralateral to the arm used for radioligand administration. Alcohol will be formulated as 6% (volume/volume) alcohol concentration in saline. The dose will be prepared by the research team. The rate of ethanol infusion, not the composition of the infusate, is the only parameter that depends on a subject's height and weight, which will be measured on the test day. Based on the height and weight, an infusion profile will be calculated to map out, step by step, what the pump rates need to be to keep a subject at the designated target blood alcohol level of 60 mg/dL. After the session subjects may drink water ad lib until scanning. Afterwards, subjects will be given dinner based on food preferences. Water, crackers, and other snacks will be available ad lib for the rest of the evening.

#### Assessments following alcohol administration:

BrAC will be measured at 15 min intervals beginning at alcohol administration and continuing until the end of scanning procedures. Vital signs will be measured concurrently. Should the measured BAC reach or exceed the targeted 60dose, then subjects will end further alcohol drinking. Other assessments that may be collected during these times include inflammation markers, self-reports of alcohol effects and mood.

1. Blood Alcohol Concentrations: Blood samples will be collected in gray stoppered (oxalate, fluoride) tubes and analyzed with gas chromatography analyses in the Yale-New Haven Hospital Clinical Laboratories. After microfuging, serum will be transferred into microtubes and stored at -20°C until assay.
2. Breath Alcohol Concentrations will be determined with an Alcohol-Sensor III (Intoximeter Inc., St. Louis, MO).
3. Inflammation Markers: Serum levels of cytokines, such as TNF- $\alpha$ , IL-1 $\beta$ , IL-4, IL-6, and IL-8, and cortisol will be measured at baseline and when blood is drawn to measure BAL. We may also collect monocytes to assess immune function *in vitro*.
4. Visual Analog Scale (VAS) self-ratings for drug effects. Subjects will answer questions to assess behavioral changes induced by substance use.
5. Subjective Effects of Alcohol Scale is a self-report measure that assesses subjective experience of alcohol effects following alcohol administration.
6. Biphasic Alcohol Effects Scale is a self-report questionnaire that assesses subjective experiences of alcohol stimulation and sedation.
7. Self-Rating the Effects of Alcohol (SRE) is a retrospective self-report questionnaire measuring the response to alcohol.
8. Columbia Suicide Severity Rating Scale (CSSRS) is a clinician administered questionnaire to assess suicidality. In the event of an unexpected outcome, subjects will be referred to the Emergency Department for risk assessment.

The total amount of blood drawn during the study will not exceed 32 tablespoons total.

#### Discharge

All participants from Aims 1, 2 and 3 will remain under observation by research staff for several hours to allow behavioral effects of alcohol to wear off. Moderate drinkers will remain under observation until BAC reading is under 20 mg/dL, at which point they are free to leave. Cab transportation will be made available. Arrangements to stay at the HRU will also be available for subjects who so choose. Individuals with alcohol use disorder will stay overnight at the CNRU and be discharged the morning following the alcohol session after confirming that vital signs are within normal limits.

A research staff member will contact subjects the following business day for a check on their health status. All subjects will be provided the telephone number of a research psychiatrist or physician on call for any problems that arise in the immediate time period after discharge from the unit. They will also be given a discharge form that has specific instructions for calling one of the physicians if they have any questions or concerns following the study.

#### 5. Genetic Testing    N/A

##### a. Describe

- i. the types of future research to be conducted using the materials, specifying if immortalization of cell lines, whole exome or genome sequencing, genome wide association studies, or animal studies are planned

We plan to use the samples to conduct pharmacogenomics studies related to the targeted neurochemical systems. The samples may also be stored for future research to examine genes related to alcohol drinking. For this we may look through genetic markers throughout the participant's genomes to identify one or more markers near, or within genes, influencing risk of alcohol drinking. We

will decode all or part of the sequence of their DNA. We may also study genes that influence other behaviors and characteristics that may be related to alcohol drinking, such as smoking or impulsivity. We may also study other substances in the blood to help us learn more about genetic variation, gene effects, characteristics, and different population groups. The DNA will also be used to study differences in genes and sequences between individuals. Results from these genetic studies will be shared with public databases (per our data sharing agreement with NIH) but no personal identifying information will be shared.

- ii. the plan for the collection of material or the conditions under which material will be received

The genetics samples will be collected at the time of physical exam from those who have consented to providing these samples. The samples will be stored in a -70 freezer prior to being de-identified and transported to the CTNA (Center for the Translational Neuroscience of Alcoholism) data repository under the supervision of [name] lab.

- iii. the types of information about the donor/individual contributors that will be entered into a database

The PI will retain identifiable information about each sample that is collected. The samples identified by code and stripped of any identifiers prior to being transported to [name] lab.

- iv. What are the methods to uphold confidentiality

The identifiers will be stored in a locked file cabinet at the PI's Office.

- b. What are the conditions or procedures for sharing of materials and/or distributing for future research projects? Genetic testing will only be conducted for research purposes and the results will be available to investigators on this study. Eventually, DNA extracted may be available to any qualified researcher; so will some of the genetic information from the DNA.

- c. Is widespread sharing of materials planned? Yes

- d. When and under what conditions will materials be stripped of all identifiers? The PI will retain identifiable information about each sample that is collected. The samples identified by code and stripped of any identifiers prior to being transported to [name] lab. All samples are made anonymous prior to distribution. Some of the investigators may have commercial interests.

- e. Can donor-subjects withdraw their materials at any time, and/or withdraw the identifiers that connect them to their materials? Donors will be told during the consenting process that they can choose to withdraw their materials at any time.

- i. How will requests to withdraw materials be handled (e.g., material no longer identified: that is, anonymized) or material destroyed)? Donors will be told to contact the PI directly to request withdrawal of participation

f. Describe the provisions for protection of participant privacy. The PI will retain identifiable information about each sample that is collected. The samples identified by code and stripped of any identifiers prior to being transported to [name] lab.

g. Describe the methods for the security of storage and sharing of materials. The identifiers will be stored in a locked file cabinet at the PI's office.

6. **Subject Population:** Provide a detailed description of the types of human subjects who will be recruited into this study.  
Up to 70 subjects (40 moderate drinkers and 30 Alcohol Use Disorder) will participate in the study. According to census figures, minority groups comprise approximately 50% of the population of New Haven (36.1% African-American, 13.2% Hispanic, 0.3% Native American, 2.4% Asian, and 4.1% other). Subjects will self-report a binge alcohol even in the previous 3 months to ensure that subject's customary drinking levels are not exceeded in the laboratory.  
All subjects will be 21-55 years of age and physically healthy. All research subjects will be recruited under guidelines of the Yale University Institutional Review Board (Human Investigation Committee). Subjects will be recruited from the community at large via IRB-approved advertising (television, newspaper, postings in community locations, Craigslist, Facebook). All participants will be screened initially on the telephone by a research assistant who will schedule the initial intake assessment. The screening and scanning sessions will involve psychological tests in the form of rating scales and questionnaires. These are all noninvasive questionnaires, e.g., to assess mood and craving, and should add no risk.

7. **Subject classification:** Check off all classifications of subjects that will be specifically recruited for enrollment in the research project. Will subjects who may require additional safeguards or other considerations be enrolled in the study? If so, identify the population of subjects requiring special safeguards and provide a justification for their involvement.

 Children	 Healthy	 Fetal material, placenta, or dead fetus
 Non-English Speaking	 Prisoners	 Economically disadvantaged persons
 Decisionally Impaired	 Employees	 Pregnant women and/or fetuses
 Yale Students	 Females of childbearing potential	

NOTE: Is this research proposal designed to enroll children who are wards of the state as potential subjects?

Yes  No

8. **Inclusion/Exclusion Criteria:** What are the criteria used to determine subject inclusion or exclusion?

**General Inclusion Criteria:**

1. Men and women, aged 21-55 years
2. Willing and able to give voluntary written informed consent
3. Able to read and write English and communicate effectively with the investigators, and comply with all study requirements, restrictions, and directions of the clinic staff
4. AUD Subjects will meet DSM-5 criteria for current Alcohol Use Disorder

5. Moderate Drinkers will report consuming alcohol on at least one occasion in the past three months that would result in an estimated blood alcohol level greater than 80 mg/dl but not meet DSM-5 criteria for AUD. This is operationally defined as more than 3 standard drinks in a single occasion for women and 4 standard drinks in a single occasion for men. This is to ensure that subjects have prior drinking exposure consistent with levels proposed in this study. Prospective subjects will be asked to recall the heaviest two days of drinking in the previous three months. Using this information, approximate BAC will be calculated for those prior episodes.
6. Medically healthy upon physical examination and laboratory testing.

**General Exclusion Criteria:**

1. Individuals whom the investigators deem may not be able to comply with alcohol abstinence for 48 hours prior to study day.
2. Current significant medical condition such as neurological, cardiovascular, endocrine, renal, liver, or thyroid pathology.
3. History of or current neurological or significant psychiatric disorder such as schizophrenia or bipolar disorder (DSM-5 Axis 1).
4. Individuals likely to exhibit clinically significant alcohol withdrawal during the study. Specifically, we will exclude subjects who a) have a history of perceptual distortions, seizures, delirium, or hallucinations upon withdrawal, or b) have a score of > 12 on the Clinical Institute Withdrawal Assessment scale at intake appointments.  
Other substance use disorder with the exception of nicotine dependence in smokers as assessed with the SCID or positive urine screen for drugs of abuse.
5. Participants with any significant current medical conditions that would contraindicate the consumption of alcohol, such as history of neurological trauma or diseases, seizures, delirium or hallucinations, hepatic, or other unstable medical conditions.
6. Current suicidal or homicidal intent or behavior, or history of suicidal or homicidal behavior, as revealed by SCID-5 evaluation, a C-SSRS will be performed if suicidality is revealed in the SCID or other questionnaires. In the event of an unexpected outcome, subjects will be referred to the Emergency Department for risk assessment. For individuals with significant suicidal ideation (i.e., intent with a plan as detailed below\*) the covering clinician (licensed clinical psychologist or psychiatrist) will be contacted immediately and a plan will be developed in collaboration with the subject, treating physician (if any), and may include inpatient hospitalization at the CNRU or referral or accompaniment to the ER.
7. No barbiturates or other known microsomal enzyme induces or inhibitors in the past month.
8. History of significant head trauma.
9. Women who are pregnant or nursing or fail to use one of the following methods of birth control unless she or partner is surgically sterile or she is postmenopausal (hormone contraceptives [oral, implant, injection, patch, or ring], contraceptive sponge, double barrier [diaphragm or condom plus spermicide], or IUD).
10. Regular or current significant use of any prescription, herbal or illegal psychotropic medications (e.g., antidepressants, antipsychotics, anxiolytics, ecstasy) in the past 6 mo, with no current illegal drug use confirmed by urine toxicology (except for cocaine and marijuana when relevant).

11. Have MRI-incompatible implants and other contraindications for MRI, such as a pacemaker, artificial joints, non-removable body piercings, claustrophobia, etc.
12. Subjects with history of prior radiation exposure for research purposes within the past year such that participation in this study would place them over FDA limits for annual radiation exposure. This guideline is an effective dose of 5 rem received per year.
13. Subjects with current, past or anticipated exposure to radiation in the work place within one year of proposed research PET scans.
14. Subjects with history of IV drug use which would prevent venous access for PET tracer injection.
15. Blood donation within eight weeks of the start of the study
16. History of bleeding disorder or currently taking anticoagulants (such as Coumadin, Heparin, Pradaxa, Xarelto).
17. Subjects whose Liver Function Tests are 4x the normal range will be excluded from the study.

\* To quantify significant suicidal ideation, we will evaluate the following items during the intake session and positive responses to the following will be used to identify individuals who should be elevated to a clinician.

-HAMD29 item #18 (3=suicidal ideas or gesture, i.e., has definite plan or cuts self, or begins to carry out suicide but stops for some reason; 4=suicide attempt during past week)

-MADRS item # 10: 5 or 6

-BDI item #9: 2 or 3

OR

-C-SSRS If they answer yes to question 2 (suicidal thoughts), we continue to ask questions 3-6 (3-without specific plan or intent to act, 4-active suicidal thoughts and some intent, 5-intent with plan, 6-suicidal behavior (collecting pills, obtaining a gun, etc.) We would elevate for a 'yes' to questions 4-6.

9. How will **eligibility** be determined, and by whom? Write here

Eligibility to participate in screening session will be determined by the research staff under the guidance of [name]. Study participation will be determined after the screening session by the study physician and [name]. There are two additional licensed clinical psychologists ([name] and [name]) and psychiatrists who are study physicians ([name] and [name]) in the group who are also available for clinical issues.

10. **Risks:** Describe the reasonably foreseeable risks, including risks to subject privacy, discomforts, or inconveniences associated with subjects participating in the research.

#### **Risks Associated with Alcohol Challenge**

Numerous medical conditions, such as liver disease, cardiac abnormality, pancreatitis, diabetes, neurological problems, and gastrointestinal disorders, could potentially be worsened by acute alcohol administration. Therefore, subjects with medical problems identified by physical exam and laboratory findings will be excluded from the study.

Another area of potential risk to subjects under the influence of alcohol is their safety during intoxication. All subjects will be under the supervision of the experimenters to prevent possible accidents such as falls. Subjects will not leave the laboratory during alcohol infusion procedures. By having the option to stay in the

CNRU or HRU overnight available, the possibility that the subject might leave the session and continue to drink alcohol, which would place them at risk for accidents, is prevented.

#### **Risks Associated with Oral Alcohol**

Alcohol may induce nausea in high doses; however, significant nausea is not expected at the targeted dose for this study because subjects will have consumed a light lunch and they will have had recent (in the last three months) experience with the targeted alcohol dose. Other side effects resulting from oral alcohol may include blurred vision, nausea, vomiting, flushing, headache, and lightheadedness. Subjects will be permitted to decline further drinking if they so choose.

#### **Risks Associated with Infusion of Alcohol**

Infused ethanol has pharmacologic effects. Side effects resulting from ethanol consumption may include blurred vision, nausea, vomiting, flushing, headache, and lightheadedness. These side effects should reach their peak within 1.5 hours following the alcohol administration and decline thereafter. Significant nausea is not expected at the targeted dose for this study because subjects will have consumed a light lunch and they will have had recent (in the last three months) experience with the targeted alcohol dose. Subjects will be permitted to decline further infusion if they so choose.

#### **Risks Associated with Use of an Arterial Catheter.**

On the PET scanning days a radial arterial catheter may be inserted. Some individuals may feel light-headed during placement of the arterial catheter. This procedure may be associated with mild-to-moderate pain, hematoma, inflammation, bleeding, or bruising at the puncture site. If any of these, or any other symptoms occur, and they do not diminish within 24 to 72 hours after removal of the arterial line, subjects will be advised to call the on-call doctor listed on the PET discharge instructions. In rare instances blocking or tearing of the artery, arterial leakage, poor healing, or infection at the catheter insertion site may occur.

Risks of radial artery cannulation are minimized by having the procedure performed **by an experienced health care provider. The health care provider would be a physician or an Advanced Practice Provider (APP): either a physician assistant (PA), or an advanced practice registered nurse (APRN) with experience in placement of arterial catheters. For an APP to place the arterial line at the Yale PET Center, they must meet the following criteria:**

- 1.) Be currently credentialed at Yale-New Haven Hospital or similar institute and
- 2.) Perform 3 arterial line procedures supervised by a currently privileged PET Center physician.

The 3 supervised arterial line placements will be documented and signed off by both the APP and supervising physician. The completed document must be on file at the Yale PET Center prior to an APP performing any arterial line catheterizations independently.

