**Risks Associated with Use of an Arterial Catheter:**

Risks of radial artery cannulation are minimized by having the procedure performed by an experienced health care provider. The health care provider would be either a physician or an advanced practice registered nurse (APRN) with experience in critical care and placement of arterial catheters, as is the practice at Yale-New Haven Hospital. For an APRN to place the arterial line at the Yale PET Center, they must meet the following criteria:

- 1.) Be currently credentialed at Yale-New Haven Hospital or similar institute and
- 2.) Perform 3 arterial line procedures supervised by a currently privileged PET Center physician

The 3 supervised arterial line placements will be documented and signed off by both the APRN and supervising physician. The completed document must be on file at the Yale PET Center prior to an APRN performing any arterial line catheterizations independently.

Pain is minimized with the use of local anesthesia. Infection is avoided by adequate cleansing of the skin before intravascular line insertion. After arterial catheter removal, bleeding is prevented by direct pressure applied to the site for a minimum of 15 minutes followed by a pressure dressing (coban) that should be kept clean and dry until evening. Subjects will have their hand and finger blood supply examined after arterial cannulation throughout the study, and again following catheter removal. Also, subjects will be asked to abstain from using aspirin and other NSAIDS for 7-10 days prior to arterial line insertion and 7-10 days following arterial line removal. Subjects will be provided a 24-hour emergency physician contact number to call if they encounter pain, discoloration, numbness, tingling, coolness, hematoma, inflammation, or any other unusual symptoms in the wrist or hand, or fever, chills or drainage from the vascular puncture sites, following the procedure. In addition, if an emergency arises at the time of cannulation or scanning, 911 will be called, and the subject will be sent to the Emergency Department for evaluation and treatment. A nurse

will provide discharge instructions outlining general instructions in addition to post-arterial catheter precautions, problems to watch for, and procedures to follow should such problems occur.

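### The arterial-line risk text ties a call to the doctor to symptoms that have not eased within 24 to 72 hours, which conflicts with the no-wait call instructions elsewhere in the protocol

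*Combined protocol and SAP*

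**What the plan says.** Three places in the combined protocol tell subjects when to seek help after the arterial line is removed.

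**Section I, item 10 (Risks), arterial catheter paragraph.** It opens with the expected local effects: "This procedure may be associated with mild-to-moderate pain, hematoma, inflammation, bleeding, or bruising at the puncture site". The call advice applies if one of those effects, "or any other symptoms occur, and they do not diminish within 24 to 72 hours after removal of the arterial line". The action is then stated: "subjects will be advised to call the on-call doctor listed on the PET discharge instructions". The rare serious harms come straight after: "In rare instances blocking or tearing of the artery, arterial leakage, poor healing, or infection at the catheter insertion site may occur". They have no call instruction of their own.

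**Section I, item 11 (Minimizing Risks), arterial catheter paragraph.** Subjects receive a "24-hour emergency physician contact number to call if they encounter pain, discoloration, numbness, tingling, coolness, hematoma, inflammation, or any other unusual symptoms" at the hand or wrist. The list ends with possible signs of infection: "fever, chills or drainage from the vascular puncture sites, following the procedure". No waiting time is attached. The same paragraph sets out the site care: "bleeding is prevented by direct pressure applied to the site for a minimum of 15 minutes followed by a pressure dressing". On circulation it says: "Subjects will have their hand and finger blood supply examined after arterial cannulation throughout the study, and again following catheter removal". A nurse also gives discharge instructions on what to look out for and what to do about it.

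**Section 4.4, Discharge.** All subjects receive the number of a research psychiatrist or on-call physician for any problem soon after leaving, and a form on how to reach a physician with questions. Staff contact them on the next business day. No waiting time is set here either.

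**The concern.** The protocol gives two timing rules for the same site. A subject with a hematoma is to call on noticing it under item 11, but is advised to call if it has not eased within one to three days under item 10. Bleeding is the more awkward case. Item 10 names it under the wait, while item 11's call list does not name it and reaches it only through the general phrase about unusual wrist or hand symptoms.

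The stake is a delayed call. Item 10 itself recognizes arterial blockage, tearing, leakage and infection as possible. Bleeding, a cold or numb hand, or a fever is how such harm could first show, and none of these should be watched for a day or more. Item 10 states what subjects will be advised and points to the PET discharge instructions, so its sentence could plausibly find its way into what subjects are handed.

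**Working it through.** There is no planned figure to reproduce. The point rests on no sample size, error rate or event count, so the check is a comparison of texts.

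**Step 1. Timing and triggers.**

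| Place | When to call | Wait | Bleeding named as a trigger? |
|---|---|---|---|
| Item 10, arterial catheter | Symptoms that have not diminished after line removal | 24 to 72 hours | Yes |
| Item 11, arterial catheter | Symptoms encountered | None | No, general phrase only |
| Section 4.4, Discharge | Any problem soon after discharge | None | No, covered by any problem |

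One of the three places sets a wait. No other section of the protocol does.

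**Step 2. Overlap of the named symptoms.**

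- Item 10 names 5: bleeding, bruising, hematoma, inflammation, pain.
- Item 11 names 10: three local signs (hematoma, inflammation, pain), four hand signs (coolness, discoloration, numbness, tingling) and three possible signs of infection (chills, drainage, fever).
- In both: 3 (hematoma, inflammation, pain). These carry conflicting timing by name.
- In item 10 only: 5 − 3 = 2 (bleeding, bruising).
- In item 11 only: 10 − 3 = 7.
- Distinct symptoms: 5 + 10 − 3 = 12.

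These counts show where the two lists meet. They count list entries, some of which overlap in meaning (bruising and discoloration, for example), and they do not measure risk.

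**Step 3. How far item 10's wait reaches.** By name it covers its own 5 symptoms. The 7 hand and infection signs that appear only in item 11 come under it solely through the catch-all for other symptoms, read literally. That catch-all carries no qualifier, so the reading is available, but it is weaker than the direct conflict on the 3 shared symptoms and the naming of bleeding.

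**Step 4. Does the next-business-day contact close the gap?** Partly. It is described as a general health check and does not mention the arterial site. Assuming weekday scanning and no weekend contact, it falls about one day after a Monday-to-Thursday scan and about three days after a Friday scan.

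**Step 5. Would narrowing the wait in item 10 be enough?** No. Suppose item 10 kept a wait for minor bruising and soreness and item 11 stayed as it is. Item 11 would still tell subjects to call without delay for pain and for discoloration, so mild pain and visible bruising would still have two rules. Bleeding would still be missing by name from item 11. Both items need to change, or item 10 has to defer to item 11.

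**The case against.** The strongest reply is that item 10 describes risks, and item 11 is where the protocol says how they are reduced. Item 11 already gives a no-wait route for every hand and infection sign, and its general phrase can be read to include bleeding. Discharge adds an on-call number for any problem. After the alcohol session, moderate drinkers stay under observation until their alcohol level is below 20 mg/dL, and subjects with alcohol use disorder stay overnight. Item 10's list also opens with a mild-to-moderate qualifier, which may govern the whole list, so the sentence can be read as a backstop for ordinary local effects that linger.

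Most of this stands, and it limits the seriousness of the point. It does not remove the conflict. Whatever the qualifier covers, hematoma and inflammation appear in item 11 with no lower limit of severity and no wait, and the catch-all in item 10 has no qualifier at all.

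Three stronger readings are tempting and are not supported:

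- **That subjects may call only after the wait.** Item 10 contains no such restriction and does not forbid an earlier call.
- **That the wait is aimed at arterial blockage, tearing or infection.** Those harms are named after the call sentence. Their signs come under the wait only if the catch-all is taken literally.
- **That subjects are in fact told to wait.** The PET discharge instructions and the consent form are not among the documents available here, so this cannot be checked, and their absence is not a fault in the plan.

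**Conclusion.** The point holds as a minor inconsistency in safety wording. Item 10 attaches a 24 to 72 hour condition to the call, while item 11 and the Discharge text attach none. The conflict is explicit for pain, hematoma and inflammation. It matters most for bleeding, which is named as a call trigger only under the wait.

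The likely harm is limited, because item 11 and Discharge already provide pressure and dressing at the site, blood-supply checks, nurse instructions, a 24-hour number and a staff contact. The documents give no complication rate, so the harm cannot be put as a number of subjects. Nothing in the statistical analysis changes.

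Confidence in the textual mismatch is high. Any practical consequence depends on the assumption that item 10's wording, or something like it, reaches subjects.

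**What to change.** 1. In item 10, replace the 24 to 72 hour condition with a cross-reference to the immediate-call list in item 11.
2. In item 11, add bleeding by name to that list.
3. If the team wishes to keep a 24 to 72 hour window, limit it to minor bruising or soreness that is not getting worse, and reword item 11 so that its pain and discoloration triggers are clearly distinguished from these.
4. Check that the PET discharge instructions and the consent form carry the same wording.

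Optionally, ask about the arterial site at the next-business-day contact already planned under Discharge.

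The cost is one sentence in item 10, a short addition to item 11 and a wording check of two subject-facing documents. There is no added visit, call or procedure, and no effect on sample size or analysis.
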